7.3. Method of Treatment Assignment

After the informed consent is signed, subjects will be assigned a subject identification number using a centralized interactive web response system (IWRS). At the Baseline Visit, a centralized schema will be applied to assign subjects who meet the inclusion and none of the exclusion criteria in a 2:1 ratio to receive either apremilast 30 mg tablets or placebo. The IWRS will stratify the randomized subjects by their use of glucocorticosteroids (yes/no) and use of a csDMARD: (csDMARD-naïve; csDMARD use prior to baseline; or csDMARD use prior to and concomitant at baseline).

Subjects who are randomized to apremilast at baseline will be dose-titrated during their first week of active treatment (see Section 7.2), while subjects who are randomized to placebo will receive identically appearing placebo titration cards while continuing to receive their assigned dose of placebo BID.

Subjects with no improvement in the swollen joint count at Week 16 are eligible for early escape. The joints monitored for early escape must correspond to those affected at baseline (sentinel joints). To maintain the study blind, placebo-treated subjects who escape early will be transitioned in a blinded fashion via an IWRS to apremilast 30 mg BID and apremilast-treated subjects will remain blinded on their original treatment assignment. Placebo subjects will be dose-titrated during their first week of active treatment (see Section 7.2), while subjects who were already on apremilast 30 mg BID will receive identically appearing placebo titration cards while continuing to receive their assigned dose of apremilast 30 mg BID.

At the Week 24 Visit, subjects will be offered to enter a 24-week Active - treatment Extension Phase (Extension Phase). All subjects enrolled in the Extension Phase will receive treatment with apremilast (30 mg BID) until the completion of the study (ie, up to the Week 48 Visit) or until early discontinuation. Placebo subjects will be dose titrated (5-day titration period). All subjects will receive treatment cards of identical appearance to maintain the blinding of the original treatment assignments (apremilast 30 mg BID or placebo).

Beginning at the Week 28 Visit, the next scheduled study visit following the placebo titration period, all subjects in the Extension Phase will be dispensed open-label apremilast (30 mg BID) in high-density polyethylene (HDPE) bottles. Subjects must be clearly instructed to follow dosing instructions.

Designated study personnel at the investigational sites will be assigned password protected, coded identification numbers, which give them authorization to log into the IWRS to randomize subjects. The system will present a menu of questions by which the study personnel will identify the subject and confirm eligibility. When all questions have been answered, the IWRS will assign a randomization identification number. Confirmation of the randomization will be sent via fax to the investigational site, Amgen and/or its representative.

During the study visits, the pharmacy or authorized study personnel at the investigational site will dispense coded IP kits in accordance with the randomization number assigned by the IWRS.

7.4. Packaging and Labeling

The label(s) for IP will include Sponsor name, address and telephone number, the protocol number, IP name, dosage form and strength (where applicable), amount of IP per container, lot

number, expiry date (where applicable), medication identification/kit number, dosing instructions, storage conditions, and required caution statements and/or regulatory statements as applicable. Additional information may be included on the label as applicable per local regulations.

All IP, including placebo and apremilast tablets, will be supplied by Amgen Inc. to the principal Investigator as blister cards during the Placebo-controlled Phase.

Starting at the Week 28 Visit, apremilast 30 mg tablets will be supplied in HDPE bottles with child-resistant caps.

7.5. Investigational Product Accountability and Disposal

The Investigator, or designee, is responsible for taking an inventory of each shipment of oral IP received, and comparing it with the accompanying IP shipping order/packing list.

The Investigator(s) or designee(s) will verify the accuracy of the information on the form, sign and date it, retain a copy in the study file, and record the information in the IRT.

Investigational product will be stored per the storage conditions identified on drug label. At the study site, all IP will be stored in a locked, safe area to prevent unauthorized access.

Amgen (or designee) will review with the Investigator and relevant site personnel the process for investigational product return, disposal and/or destruction including responsibilities for the site versus Amgen (or designee).

7.6. Study Medication Dispensing and Counting

After the subject has satisfied all inclusion and exclusion criteria, study medication will be dispensed as specified in Table 13, Table of Events. The tear-off label from each blister card should be pasted into the drug accountability document in each subject's record. Subjects must be instructed to return all previously issued empty blister card(s), empty study drug bottle(s) and/or unused study medication at the time that new medication is issued. A detailed record of tablets issued and returned at each visit must be maintained in the subject's record.

Amgen (or designee) will review with the Investigator and relevant site personnel the process for investigational product return, disposal, and/or destruction including responsibilities for the site versus Amgen (or designee).

7.7. Investigational Product Compliance

Study personnel will review the instructions printed on the package with the study subjects prior to dispensing the IP. Investigational Product will be dispensed as noted in Table 13, Table of Events. The subjects will be instructed to return the IP containers, including any unused medication, to the study site at each visit for tablet counts and reconciliation. Subjects will be asked whether they have taken their IP as instructed at each study visit. Any problems with IP compliance will be reviewed with the subject. If subject misses 4 or more consecutive days of dosing, Amgen must be contacted to decide whether dosing should resume or whether the subject should be terminated from the Treatment Phase of the study and enter the Observational Follow-up Phase.

Gross compliance problems (eg, missing 4 or more consecutive days of dosing or taking less than 75% of the doses between study visits) should be discussed with Amgen. Compliance is defined as taking between 75% and 120% of dispensed IP.

7.8. Overdose

Overdose, as defined for this protocol, applies to protocol-required dosing of the investigational product(s) (IPs) only. Therefore, for a drug to be subject to the overdose definition it must be *both required* and an *investigational drug*. In this study the only required and investigational drug is apremilast and the control arm drug (ie, placebo), hence overdose definition will apply to only apremilast (or matching placebo). Other required or optional non-study drugs intended for prophylaxis of certain side effects, etc, are excluded from this definition.

Overdose for this protocol, on a per dose basis, is defined as ingestion of 4 or more 30 mg apremilast (or matching placebo) tablets in any 24-hour period, whether by accident or intentionally. On a schedule or frequency basis, an overdose is defined as dosing more than 4 times during any 24-hour period.

Adverse Events associated with an overdose must be collected on the Adverse Events page of the eCRF (see Section 10) for all overdosed subjects, but the overdose itself is not considered an AE. If the AE associated with the overdose meets seriousness criteria, it must also be reported to Amgen Global Patient Safety using the paper SAE report form (see Section 10.5).

8. CONCOMITANT MEDICATIONS AND PROCEDURES

All medications (prescription and non-prescription), treatments and therapies taken by the subject from screening throughout their entire participation in the study, including those initiated prior to the start of the study, must be recorded on the subject's source document and on the appropriate page of the eCRF. The dose, unit, frequency, route, indication, the date the medication was started and the date the medication was stopped (if not ongoing) must be recorded. Subjects may continue receiving standard of care therapy (eg, folic acid for those on MTX) if not explicitly prohibited as per protocol. Additional instructions can be found in the electronic Case Report Form (eCRF) Completion Guidelines.

8.1. Permitted Concomitant Medications and Procedures

The following concomitant medications and procedures are permitted during the study:

- Oral glucocorticosteroids are to be taken on a stable dose up to the Week 24 Visit:
 - Prednisone ≤ 10 mg/day (or prednisolone equivalent) for at least 4 weeks prior to the Baseline Visit must be continued and maintained through the Week 24 Visit (change in dose and/or discontinuation are not allowed except for safety reasons or for lack of availability).
- NSAIDs (and/or narcotic analgesics) are allowed during the study, provided that the NSAIDs are taken on a stable dose for at least 2 weeks prior to the Baseline Visit.
 - The stable dose of NSAIDs or narcotic analgesics must be continued and maintained from the Baseline Visit through the Week 24 Visit. Change in doses, increase or decrease, and/or discontinuation of NSAIDs or narcotic analgesics will not be allowed except for safety reasons or for lack of availability. After the Week 24 Visit, the dose of NSAIDs or narcotic analgesics may be adjusted as clinically required.
 - NSAIDs or narcotic analgesics that are administered on an as needed basis (PRN) should be recorded on the Prior/Concomitant Medications page of the eCRF.

• csDMARDs –

- Only 1 csDMARD (MTX or SSZ) for the treatment of PsA is permitted during the first 24 weeks of the study, provided that the treatment is taken on a stable dose ≥ 3 months prior to the Baseline Visit.
- Subjects exposed to MTX or SSZ and stopped treatment due to intolerance or due to safety reasons may enter the study provided that treatment was stopped within at least 4 days of the Baseline Visit
 - The allowed dose for permitted csDMARDs are: MTX (oral or parenteral) ≤ 25 mg/week; SSZ (oral) ≤ 3 gm/daily
- Low-dose aspirin (acetylsalicylic acid, up to 325 mg per day) for cardiovascular prophylaxis.
- Loperamide and antidiarrheal drugs with antisecretory effect (eg, racecadotril).

Protocol CC-10004-PSA-013

• A nonmedicated skin emollient (eg, Eucerin® cream) for body psoriasis lesions only.

After the Week 24 Visit, changes in the following therapy will be permitted as clinically required for subjects with worsening arthritic symptoms of PsA:

- Change of NSAID type and/or dose
- Parenteral glucocorticoids are allowed, provided that the following criteria are met:
 - Administration of no more than 40 mg intra-articular (IA) or intra-muscular (IM) glucocorticosteroid (triamcinolone hexacetonide or equivalent) injection at a single visit.
 - o Injected joints should not be counted during the visits that will take place within 4 weeks of the intra-articular injection. Joints should be marked with an X.
 - o Intra-articular injection should not be performed after week 44 visit (ie, ≤4 weeks prior to study end).
- Oral glucocorticosteroids may be adjusted as clinically required
 - o Short course (≤ 2 weeks) of oral corticosteroids, including a Medrol Dosepak[®], not to exceed one course in any 6-month interval
- Non-biologic DMARDs: methotrexate (≤ 25 mg/week), sulfasalazine (≤ 3 gm/day), leflunomide (≤ 20 mg/day), hydroxychloroquine (≤ 400 mg/day), chloroquine (≤ 600 mg/day).

After Week 24, if subjects experience a decrease in PsA clinical disease activity, the Investigator may opt to taper the background treatment; however, only one agent may be reduced or tapered at any one time. After the first agent has been tapered (not required to be zero), the dose must be stable for at least 4 weeks prior to tapering the next agent. Subjects are recommended to have a reduction of background therapy in the following order (when applicable): First csDMARD, second glucocorticosteroids and third NSAIDs or other pain medication. If clinically indicated, the Investigator may opt to reduce the medications in a different order. Any further questions/concerns regarding dose reductions can be discussed with the Sponsor.

In order to minimize the impact on ongoing efficacy assessments, the investigator should use the least intensive regimen to ameliorate the subject's worsening PsA symptoms.

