6.4.1.1. Joint Assessment

A modified joint count that includes the distal interphalangeal joints of the fingers and toes (the "68 tender and 66 swollen" joint scores; (Appendix D) will be performed at every visit. Joint tenderness and swelling will be noted as "present" or "absent," with no quantitation of severity. In case of digit(s) with dactylitis, each joint of the affected digit must be evaluated for tenderness and swelling.

Joints that are swollen or tender should be marked with a "tick". In the event that a joint is injected with intra-articular or intra-muscular glucocorticoid (allowed only after Week 24 assessments are completed, and up to the Week 48 Visit), this joint should be marked by an "X" and won't be assessed if the study visit occurs within 4 weeks (28 days) of the intra-articular (IA) injection. In order to maintain consistency throughout the study, the same evaluator should perform the joint assessments for a given subject at a study site at each study visit.

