Appendix D: Joint Assessment - 68 and 66 Joint Counts

68 Joint Score: Upper Extremity Joint Counts

Please write in the appropriate code for every joint using the Pain/Tenderness and Swelling Codes.

Pain/Tenderness Codes Swelling Codes

 $egin{align*} N &= \mbox{No pain/tenderness} & N &= \mbox{No swelling} \\ Y &= \mbox{Pain/tenderness} & Y &= \mbox{Swelling} \\ ND &= \mbox{Not Done} & ND &= \mbox{Not Done} \\ \end{align*}$

Joints that are swollen and tender should be marked with a tick. If a joint is injected with intraarticular glucocorticoid, this joint should be marked by an X for the next 4 weeks

	Right Side		Left Side	
Joints	Pain/Tenderness	Swelling	Pain/Tenderness	Swelling
	Y N ND	Y N ND	Y N ND	Y N ND
Temporomandibular				
Sternoclavicular				
Acromioclavicular				
Shoulder				
Elbow				
Wrist				
MCP 1				
MCP 2				
MCP 3				
MCP 4				
MCP 5				
PIP 1				
PIP 2				
PIP 3				
PIP 4				
PIP 5				
DIP 2				
DIP 3				
DIP 4				
DIP 5				

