#### 5.1.2 Joint Assessment

TJC or SJC will be derived from the joint assessments entered by the physician via tablets provided by ERT. Joint assessment for tenderness and swelling will be performed for 68 and 66 joints (Appendix D of Protocol), respectively, at every visit. Joint tenderness and swelling will be noted in the following categories, with no quantitation of severity, as shown on the tablet.

- Pain/Tenderness Only
- Swelling Only
- Pain/Tenderness and Swelling
- Permanently Not Assessable
- Temporarily Not Assessable Due to IA Injection
- Temporarily Not Assessable Other

In the event that a joint is injected with intra-articular (IA) glucocorticoid (allowed only after week 24 assessments are completed, and up to the Week 48 Visit), this joint should be marked as "Temporarily Not Assessable Due to IA Injection" if the study visit occurs within 4 weeks (28 days) of the IA injection. In order to maintain consistency throughout the study, the same evaluator should perform the joint assessments for a given subject at a study site at each study visit.

As a joint assessment may be recorded as "temporarily not assessable" or "permanently not assessable", the following data handling rules will be applied to handle the data in the calculation of SJC and TJC.

 Joints temporarily or permanently not assessable at baseline are excluded from joint count throughout the study.

Protocol Number: 20200058
Date: 07 February 2023
Page 22 of 67

 For other un-assessed joints at baseline, the joint assessment at the screening visit, if assessed, is used as the baseline assessment; otherwise, the joint is excluded from joint count throughout the study.

For joints that become either temporarily or permanently not assessable at a
post-baseline visit, the last observed joint assessment (including baseline and
post-baseline assessments) will be used for that visit.

After applying these data handling rules, TJC will be calculated by adding the number of joints with outcomes of 'Pain/Tenderness Only' or 'Pain/Tenderness and Swelling'. SJC will be calculated by adding the number of joints with outcomes of 'Swelling Only' or 'Pain/Tenderness and Swelling'. TJC and SJC will be derived based on the sentinel joints and all joints (66 joints for swelling and 68 joints for tenderness).

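### Protocol and SAP conflict on the extension-phase joint injection cut-off and on how an injected joint is counted, so descriptive Week 28, 40 and 48 joint results can turn on which text is followed

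*Protocol*

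**What the plan says.** **Cut-off.** Protocol Section 8.1, on medication changes permitted after Week 24 for worsening arthritic symptoms, says: "Intra-articular injection should not be performed after week 44 visit (ie, ≤4 weeks prior to study end". Protocol Section 6.4.1.1, which names both the intra-articular and the intramuscular route, describes injection as "allowed only after Week 24 assessments are completed, and up to the Week 48 Visit". SAP Section 5.1.2, which names only intra-articular injection, allows it "after week 24 assessments are completed, and up to the Week 48 Visit". Neither Protocol Table 13 nor SAP Appendix A lists a Week 44 visit; the extension visits are Weeks 28, 40 and 48. Section 8.1 permits intramuscular injection too, but its cut-off sentence covers only the intra-articular route.

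**Handling of an injected joint.** Protocol Section 8.1: "Injected joints should not be counted during the visits that will take place within 4 weeks of the intra-articular injection". Protocol Section 6.4.1.1 says the joint will not "be assessed if the study visit occurs within 4 weeks (28 days) of the intra-articular (IA) injection", and Appendix D says "this joint should be marked by an X for the next 4 weeks". SAP Section 5.1.2 has a separate code for a joint that is temporarily not assessable because of intra-articular injection. For any joint that becomes temporarily or permanently not assessable after baseline, it substitutes "the last observed joint assessment (including baseline and" later assessments) at that visit, and then adds the joint into SJC and TJC. It makes no exception for injected joints.

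**The concern.** There are two separate conflicts. First, sites reading different sections can inject in different periods just before the last efficacy visit, and one of the limits refers to a visit that does not exist. Second, leaving a joint out of the count and counting it at its last status cannot both apply, so the same subject can be a responder under one document and a non-responder under the other.

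Beneath the second conflict lies an issue that both rules share. Injections in this phase are given for worsening symptoms. A joint that was quiet at its last recorded assessment, then flared and was injected, enters the next count as not active.

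Subjects enter with 2 to 4 swollen and 2 to 4 tender joints, and the joint-count analyses use sentinel joints, so a single joint can sometimes decide SJC ≤ 1, TJC ≤ 1 and hence MDA-Joints. At stake is how the extension results on long-term efficacy are read.

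**Working it through.** The plan gives no figure on this point to reproduce. The check is date arithmetic and a comparison of the counting rules.

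**Step 1. Inputs.** Target days from SAP Appendix A, Table 5: Week 24 = 169, Week 28 = 197, Week 40 = 281, Week 48 = 337. The Week 48 visit window is ±1 week (Protocol Table 13). The non-assessment period is 28 days (Protocol Section 6.4.1.1, SAP Section 5.1.2). The joint criterion is a count ≤ 1.

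**Step 2. The two cut-offs.** Week 44 is day 44 × 7 + 1 = 309, and 337 − 309 = 28. The permitted periods therefore differ by the last four weeks before the final visit. Section 8.1 is also ambiguous at its own boundary: day 309 is not after Week 44, yet it is within 4 weeks of day 337.

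**Step 3. Which visits can be affected.** An injection on day d makes a joint not assessable at a visit on day V if V − 28 ≤ d ≤ V − 1.

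| Visit (nominal day) | Injection days, Week 44 limit | Injection days, Week 48 limit |
|---|---|---|
| Week 28 (197) | 169–196 | 169–196 |
| Week 40 (281) | 253–280 | 253–280 |
| Week 48 (337) | 309 only | 309–336 |

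If the Week 48 visit falls 7 days early (day 330), days 302–309 qualify even under the Week 44 limit. So Weeks 28 and 40 are exposed whichever cut-off holds, and Week 48 is exposed mainly under the later one.

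**Step 4. The counting rules.** Take three sentinel joints: A active, C inactive, and B injected within 28 days of the visit.

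| Joint B at last record | Protocol 8.1 (not counted) | SAP 5.1.2 (carried forward) | B counted as active |
|---|---|---|---|
| Active | 1, met | 2, not met | 2, not met |
| Inactive, then flared | 1, met | 1, met | 2, not met |

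Row 1 is the conflict between the documents. Row 2 is the problem that both rules share.

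**Step 5. When status flips.** With k other active sentinel joints and one injected joint scored b = 0 or 1, the criterion is k + b ≤ 1. For k = 0 it is met either way (0 or 1). For k ≥ 2 it fails either way. Only k = 1 flips. MDA-Joints also needs 3 of the 5 remaining criteria.

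**Step 6. Weight of one subject.** SAP Section 6.7.1 tabulates by randomized group. About 285 subjects at 2:1 gives 190 and 95. One reclassified subject moves a rate by 100/190 = 0.53 points in the apremilast group and 100/95 = 1.05 points in the placebo-origin group, or more if fewer subjects are in the denominator. How many subjects would be reclassified cannot be derived from the documents.

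**The case against.** The strongest reply is that the reach is small. Injection is allowed only after the Week 24 assessments. The primary endpoint, every secondary efficacy endpoint and the testing hierarchy are at Week 16. After Week 24 everyone who continues receives apremilast, and Protocol Section 9.6.5 plans descriptive summaries only. This stands. A reader might infer that the main efficacy claim is at risk, and the documents do not support that.

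A reader might also infer that SAP carry-forward is what turns flares into responses, so that following the protocol would cure it. Step 4 shows otherwise: leaving the joint out never gives a higher count than carrying it forward, so the SAP rule is equal or stricter. A joint scored active at a visit and then injected stays active under the SAP. A count at an unscheduled visit (Protocol Section 6.2) might also be picked up, although SAP Section 5.4 limits time-point analysis to scheduled visits and leaves this unclear.

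An injection at Week 45, the most striking illustration, is barred by Section 8.1, and Section 8.3 points to 8.1 for post-Week 24 injections. The example is compliant only under the other two texts.

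Protocol Section 9.1 assigns data handling and imputation to the SAP. That reconciles a site not assessing a joint with an analysis that imputes it. It does not reconcile not counting the joint with counting it.

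The wording in Section 6.4.1.1 about marking a joint after intramuscular injection looks odd but has no analytic effect, since the 28-day clause and the SAP code name only the intra-articular route.

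Finally, the exploratory endpoints and SAP Section 9.5.3 are redacted, so a further handling rule or sensitivity analysis may exist there. The visible conflict remains either way.

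**Conclusion.** The point holds as a conflict between current texts with limited analytic reach. The injection cut-offs differ by 28 days, one is tied to a visit that is not scheduled, and the cut-off in Section 8.1 is silent on the intramuscular route. The two handling rules give different responder status when one other sentinel joint is active and the injected joint was last seen active. Both rules score a newly flared, injected joint as not active if its last record was inactive.

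Only the descriptive joint-based results at Weeks 28, 40 and 48 are affected. A reader might put a number on the bias: if 5% of subjects are injected within 28 days of a visit and half of those joints were last seen inactive, 5% × 0.5 = 2.5 points, or 1 to 5 points for 2% to 10% injected. Those rates are assumptions with no support in the documents, and the result is a ceiling, because it takes every such subject to change status when Step 5 shows that most configurations do not. The size is unknown.

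**What to change.** 1. Reconcile Protocol Sections 8.1 and 6.4.1.1 and SAP Section 5.1.2 on the injection cut-off. Tie it to a visit or study day that exists and state what applies to each route. Which cut-off is right is a clinical decision on which this review takes no position.
2. State one rule for how an injected joint enters SJC and TJC, and use it in both documents.
3. In the SAP, show the extension joint-based response rates a second time, with joints carrying the code for not assessable due to intra-articular injection counted as active at that visit, beside the carry-forward result. This covers row 2 of Step 4, which reconciling the wording alone would leave in place.

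The cost is wording in two protocol sections and one SAP rule, plus one extra descriptive display. The injection code is already captured in the joint assessment, so no new data are needed. The downside is that extension response rates may look slightly less favourable in the second display.
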